1.0 ABBREVIATIONS

| | |
|------------|---|
| 5-FU | 5-fluorouracil |
| BPI | Brief pain inventory |
| CRF | Case report form |
| CIPN | Chemotherapy-induced peripheral neuropathy |
| CRS | Clinical Research Support |
| CTCAE | Common Terminology Criteria for Adverse Events |
| DSMP | Data and Safety Monitoring Plan |
| DSMC | Data and Safety Monitoring Committee |
| EOT | End-of-treatment |
| FOLFIRINOX | |
| FOLFOXIRI | 5-FU, oxaliplatin, irinotecan |
| FOLFOX | 5-FU, oxaliplatin |
| IRB | Institutional Review Board |
| GI | Gastrointestinal |
| SNRI | Selective serotonin-norepinephrine reuptake inhibitor |
| SRC | Scientific Review Committee |
| SSRI | Selective serotonin reuptake inhibitor |
| TCM | Traditional Chinese Medicine |
| UW | University of Washington |

2.0 PROTOCOL SYNOPSIS

| | |
|---------------------|--|
| Protocol Title | Pilot study of oral cryotherapy vs. oral cryotherapy plus acupuncture and acupressure to decrease chemotherapy-induced peripheral neuropathy from oxaliplatin-based chemotherapy for GI cancers |
| Protocol Number | Pending |
| Protocol Funding | Safeway Early Career/Cancer Center Support Grant Pilot Award |
| Trial Phase | Phase II |
| Trial Type | Randomized Control Feasibility Trial |
| Clinical Indication | GI cancer for which a new oxaliplatin-based regimen is recommended |
| Study Objectives | 
Primary: To evaluate the severity of CIPN in GI cancer patients receiving oxaliplatin-based chemotherapy following 3 months of acupuncture/acupressure treatment plus oral cryotherapy compared to oral cryotherapy alone.
 
Secondary 1: To estimate the incidence of grade 2 or higher CIPN in GI cancer patients receiving oxaliplatin-based chemotherapy following 3 months of acupuncture/acupressure treatment plus oral cryotherapy compared to oral cryotherapy alone.
 
Secondary 2: To evaluate the severity of CIPN in GI cancer patients receiving oxaliplatin-based chemotherapy following 3 months of acupuncture/acupressure treatment plus oral cryotherapy compared to oral cryotherapy alone using objective measurement tools.
 
Secondary 3: To assess the feasibility of delivering acupuncture during biweekly chemotherapy infusion and the feasibility of patient self-administered acupressure between infusions.
 
Secondary 4: To evaluate the effect of oral cryotherapy with acupuncture/acupressure vs. oral cryotherapy alone in reducing pain, fatigue, nausea, oral dysesthesia, and anxiety in GI cancer patients receiving oxaliplatin-based chemotherapy.
 |
| Study Design | Randomized Controlled Feasibility Trial |
| Population | 56 patients with a GI cancer malignancy with planned ≥3 months of a 5-FU- and oxaliplatin-based chemotherapy regimen. Eligibility criteria includes: 1) GI cancer (primary esophagus, gastric, pancreas, biliary, small bowel, appendix, colon, or rectal) scheduled to receive a new start of 5-FU, oxaliplatin, ± irinotecan [FOLFOX, FOLFIRINOX, FOLFOXIRI regimens] with plan for ≥3 months of therapy with the regimen, 2) age ≥18 years, 3) absolute neutrophil count >500 and platelet count >20,000, 4) not currently pregnant, 5) ability to understand and the willingness to sign a written informed consent document, 6) no baseline neuropathy from any cause, 7) no prior neurotoxic chemotherapy of any kind in the prior 3 years, 8) no planned initial dose of oxaliplatin <100% of the standard regimen-specified dose, 9) no receipt of acupuncture treatment in the prior 3 months, 10) no use of concomitant duloxetine for minimization of neuropathy, 11) no psychiatric illness/social situations that would limit compliance with study requirements. |
| Primary Endpoint | Chemotherapy-induced peripheral neuropathy as measured by the EORTC-CIPN 20. |
| Secondary Endpoints | 
 Incidence of grade 2 or higher CIPN as measured by CTCAE version 5. Severity of chemotherapy-induced peripheral neuropathy as measured by a Neuropen and tuning fork. Proportion of patients assigned to the intervention arm who complete 60% of acupuncture treatments. Incidence of pain, fatigue, nausea, oral dysesthesia, and anxiety as measured by the NCI PRO-CTCAE, Brief Pain Inventory (BPI), and CTCAE version 5. |

| | |
|-----------------------------|--|
| Type of control | Usual care + waitlist arm – receives no acupuncture during the 3-month intervention period |
| Investigation Drug | N/A |
| Dose | Acupuncture: 12 treatments with 30-minute needle retention |
| Route of administration | Acupuncture: filiform needle insertion |
| Regimen | 12 sessions of acupuncture. Acupressure training and self-treatment. |
| Trial Blinding | None |
| Treatment Groups | Arm A: Acupuncture + Acupressure Intervention with standard-of-care cryotherapy: acupuncture during chemotherapy infusion (day 1) and 5-FU pump disconnect (day 3) of each biweekly chemotherapy infusion x6 cycles (i.e. 12 acupuncture treatments over 12 weeks) + self-acupressure Arm B: Waitlist Control Arm with standard-of-care cryotherapy: 6 acupuncture sessions after the completion of the trial |
| Treatment Schedule | Days 1 and 3 of each chemotherapy treatment cycle |
| Efficacy Assessments | Baseline 6 weeks 12 weeks |
| Number of trial subjects | 56 |
| Estimated duration of trial | 24 months |
| Duration of Participation | 3 months |

4.0 GENERAL INFORMATION

1.1 Protocol Title

Pilot study of oral cryotherapy vs. oral cryotherapy plus acupuncture and acupressure to decrease chemotherapy-induced peripheral neuropathy from oxaliplatin-based chemotherapy for GI cancers

5.0 INTRODUCTION TO THE PROTOCOL

5.1 Introduction

Chemotherapy-induced peripheral neuropathy (CIPN) negatively impacts treatment delivery, both acutely (by requiring dose reductions, delays, or requiring early cessation of treatment) and chronically (by impacting quality of life for survivors). CIPN is a common side effect of oxaliplatin, which is a component of the majority of standard adjuvant and/or first-line metastatic therapies for gastroesophageal, pancreas, and colorectal cancer patients. In the MOSAIC trial of adjuvant 5-fluorouracil (5-FU) and oxaliplatin [FOLFOX], >90% of colon cancer patients reported CIPN during treatment, with 15% reporting symptoms four years later.¹ Similarly, in pancreas cancer patients receiving six months of 5-FU, irinotecan, and oxaliplatin [FOLFIRINOX] in the adjuvant setting, 61% had any-grade CIPN and 9-10% had grade 3+ CIPN in the landmark adjuvant and metastatic trials.^{2, 3} The high prevalence of acute and persistent CIPN in multiple gastrointestinal (GI) cancer patient populations highlights the need to more effectively mitigate acute and chronic CIPN.

In addition to peripheral neuropathy symptoms, as a result of oxaliplatin administration, patients can experience oral dysesthesia, which can negatively impact oral intake. Patients are typically educated to avoid cold foods and fluids, which can significantly impact food choices and eating/drinking overall during the acute symptoms of neurotoxicity.⁴ This is especially problematic in GI cancers, where digestion and oral intake are often compromised by the cancer itself.

Complementary therapies have been tested in the prevention and treatment of CIPN, with few effective treatments identified.⁵ Calcium and/or magnesium infusions with oxaliplatin were standard-of-care for prevention of CIPN, but were unsupported by a large randomized trial.⁶ Newer efforts have included both cryotherapy and acupuncture.

5.2 Clinical Data with Cryotherapy

Oral ice chip cryotherapy has recently been introduced as a method to prevent oral thermal hyperalgesia, thought to be mediated by vasoconstriction.⁷ In this single institution study, 62 patients were randomized and 50 were evaluable (having received at least 2 cycles) for either oral ice chip cryotherapy, delivered for 120 minutes during oxaliplatin infusion versus a control group, who was asked to avoid ingesting anything cooler than room temperature for the duration of the infusion. Using a scoring system, the ice chip cryotherapy intervention group had less oral and peripheral neuropathy symptoms prior to cycle 2 as compared to the control group. This was also demonstrated longitudinally. The benefit from oral ice chip cryotherapy was dose-dependent, meaning that longer ice duration was associated with less CIPN. Based on this data, ice chip cryotherapy (in the form of oral ice, hand/foot ice packs) was adopted into standard clinical practice.

5.3 Clinical Data with Acupuncture and Acupressure

Acupuncture has been explored as a safe nonpharmacological method of preventing and treating CIPN. The mechanisms of acupuncture are not fully understood. Acupuncture has been shown to work by adjusting neurophysiologic and neurohormonal activity.^{8, 9} Prior trials have had inconsistent results, likely due to differences in acupuncture protocols, use of electroacupuncture, timing of intervention, choice of comparator, and sample size, but the recent data suggests promise for using acupuncture for CIPN prevention.¹⁰⁻¹⁵

Acupressure has also demonstrated efficacy in decreasing fatigue, nausea, pain and improving quality of life in cancer patients.¹⁶⁻²¹ A 2019 Systematic Review and Meta-Analysis found a moderate level of evidence that acupuncture and/or acupressure compared to a sham control were significantly associated with lower intensity in cancer-related pain inpatients with cancer, which suggests a potential for a combination of acupuncture with acupressure to reduce the amount of cancer-related pain that may require opioid use as a treatment.²¹ Acupuncture and acupressure have potential to be scalable treatments for CIPN because they are both reproducible and standardized. Acupressure is an inexpensive and easy-to-perform self-care intervention.

5.4 Risks/Benefits

Oral cryotherapy and acupuncture have yet to be systemically tested together to assess this combination for maximal prevention of the onset and progression of CIPN. However, it is well recognized that CIPN can have acutely and chronically negatively impact quality of life. As there are few effective treatments outside of withdrawing the offending agent, prevention and minimization of neuropathic toxicities is highly necessary.

6.0 OVERVIEW OF CLINICAL TRIAL

6.1 Study Objectives

6.1.1 Primary Objectives

To evaluate the severity of CIPN in GI cancer patients receiving oxaliplatin-based chemotherapy following 3 months of acupuncture/acupressure treatment plus oral cryotherapy compared to oral cryotherapy alone.

6.1.2 Secondary Objectives

- 1: To estimate the incidence of grade 2 or higher CIPN following 3 months of acupuncture/acupressure treatment plus oral cryotherapy compared to oral cryotherapy alone.
- 2: To evaluate the severity of CIPN in GI cancer patients receiving oxaliplatin-based chemotherapy following 3 months of acupuncture/acupressure treatment plus oral cryotherapy compared to oral cryotherapy alone using objective measurement tools.
- 3: To assess the feasibility of delivering acupuncture during biweekly chemotherapy infusion and the feasibility of patient self-administered acupressure between infusions.
- 4: To evaluate the effect of oral cryotherapy with acupuncture/acupressure vs. oral cryotherapy alone in reducing pain, fatigue, nausea, oral dysesthesia, and anxiety in GI cancer patients receiving oxaliplatin-based chemotherapy.

6.2 Study Population

Patients with a GI cancer malignancy with planned ≥3 months of a 5-FU- and oxaliplatin-based chemotherapy regimen.

6.3 Study Design

6.3.1 Primary Endpoint

Severity of CIPN as measured by the EORTC-CIPN 20.

6.3.2 Secondary Endpoints

Incidence of grade 2 or higher CIPN as measured by CTCAE version 5.

Severity of CIPN as measured by a Neuropen and tuning fork.

Proportion of patients assigned to the intervention arm who complete 60% of acupuncture treatments.

Incidence of pain, fatigue, nausea, oral dysesthesia, and anxiety as measured by the NCI PRO-CTCAE, BPI, and CTCAE version 5.

6.4 Estimated Accrual

Fifty-six patients will be enrolled, 28 randomized to each arm.

6.5 Name of Sponsor/Funding Source

This study is funded by a Safeway / Cancer Center Support Grant Pilot Award.

7.0 SUBJECT ELIGIBILITY

7.1 Inclusion Criteria

7.1.1 GI cancer (primary esophagus, gastric, pancreas, biliary, liver, small bowel, appendix, colon, rectal, anal, or gastrointestinal/pancreatic neuroendocrine tumor) scheduled to receive a new start of 5-FU, oxaliplatin, ± irinotecan [FOLFOX, FOLFIRINOX, FOLFOXIRI regimens] with plan for ≥3 months of therapy with the regimen

Chemotherapy can be given for neoadjuvant, adjuvant, or palliative intent.

1 dose (cycle) of the intended regimen is permitted prior to study enrollment. There is no limitation on the addition of a biologic agent to one of the above chemotherapy regimens, including, but not limited to: bevacizumab, cetuximab, panitumumab, trastuzumab, or the biosimilars of these agents.

- 7.1.2 Age \geq 18 years**
- 7.1.3 Absolute neutrophil count >0.5 thousand/microL and platelet count >20 thousand/microL**
- 7.1.4 Not currently pregnant**
- 7.1.5 Ability to understand and the willingness to sign a written informed consent document.**

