7.2 Exclusion Criteria

- 7.2.1 Baseline peripheral neuropathy from any cause**
- 7.2.2 Planned oxaliplatin with capecitabine**
- 7.2.3 Planned initial dose of oxaliplatin $<100\%$ of the standard regimen-specified dose**
For most regimens, this would be 85mg/m² IV dosed every 14 days.
- 7.2.4 Receipt of acupuncture treatment in the prior 3 months**
- 7.2.5 Use of concomitant duloxetine for minimization of neuropathy.**
- 7.2.6 Psychiatric illness/social situations that would limit compliance with study requirements.**

[figure not shown]

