9.1 Treatment Plan Overview

9.2 Acupuncture and Acupressure Intervention

The intervention group will receive acupuncture during chemotherapy infusion (day 1) and 5-FU pump disconnect (day 3) of each biweekly chemotherapy infusion x6 cycles (*i.e.* 12 acupuncture treatments over 12 weeks). Acupuncture treatments will be specifically targeted to prevent, treat, or mitigate neuropathy symptoms, pain, fatigue, nausea and anxiety. Patients will receive 30-minute acupuncture treatments in the seated or supine position. Standard acupoint techniques for point location²² will be utilized and Clean Needle Technique²³ will be followed using 32-40-gauge x 30-40mm Seirin acupuncture needles.

On day 1 the acupuncture points will be needled bilaterally at: ST36, SP6, LI10, GB40, P6, auricular shen men, and on the midline at Yin Tang (EX-HN3) and GV20. On day 3 the acupuncture points will be needled bilaterally at: LI4, LR3, ST36, SP6, LI10, GB40, P6, auricular shen men, and on the midline at Yin Tang (EX-HN3) and GV20. For patients unable to tolerate peripheral cryotherapy, the day 3 acupuncture protocol will be administered on day 1.

After the initial acupuncture treatment, the study acupuncturist will instruct the patient on how to locate and self-administer acupressure for key acupoints: bilateral LI4 (for pain, oral dysesthesia), bilateral P6 (nausea), and midline GV20 (fatigue). These acupoints are based on previously published studies,¹²⁻¹⁵ Traditional Chinese Medicine (TCM) theory,²² and current understanding of innervation and neuromodulation of acupoints.¹³ Auricular shen men points (anxiety) will be stimulated with vaccaria seeds applied by the acupuncturists on day 3 and removed after 4 days (day 7 of the cycle). Patients will be taught to self-administer an 11-minute acupressure regimen daily by stimulating each acupoint in a circular motion for 2 minutes on each bilateral points of LI4 and P6, 2 minutes on midline GV20, and to gently press the ear seeds on shen men for 30 seconds three times per day. The acupuncturists will provide additional teaching during the acupressure training on Cycle 1 Day 1 instructing the patients to utilize auricular Shen Men point during cryotherapy to help mitigate possible unpleasant effects of cryotherapy including: headache, toothache, and/or cold aversion/pain.

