16.4 Randomization

Patients will be randomized 1:1 between the intervention arm and control arm.

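### Eligibility allows one oxaliplatin cycle before enrollment without requiring six cycles to remain, and neither randomization nor the primary model accounts for that cycle

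*Combined protocol and SAP*

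**What the plan says.** Section 7.1.1 admits patients scheduled for a new start of a 5-FU and oxaliplatin regimen "with plan for ≥3 months of therapy with the regimen", and then states that "1 dose (cycle) of the intended regimen is permitted prior to study enrollment". It does not say that the 3 months run from enrollment, or that any number of cycles must remain. For cycle length and dose, section 7.2.3 says "For most regimens, this would be 85mg/m² IV dosed every 14 days".

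Section 9.2 delivers acupuncture on day 1 and day 3 "of each biweekly chemotherapy infusion x6 cycles", giving 12 sessions over 12 weeks. Section 7.2.1 excludes "Baseline peripheral neuropathy from any cause", but section 7.2 does not exclude the one prior dose. The synopsis, however, lists "no prior neurotoxic chemotherapy of any kind in the prior 3 years", a criterion that sections 7.1 and 7.2 do not carry.

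On allocation, section 16.4 says only that "Patients will be randomized 1:1 between the intervention arm and control arm". Section 16.5 compares the 3-month CIPN-20 score by linear regression adjusted for baseline severity and declines further covariates because this is a pilot. Delivered chemotherapy dose intensity is to be noted, but it has no role in the comparison.

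**The concern.** The primary objective is CIPN severity after 3 months of an intervention meant to prevent it during oxaliplatin. Patients who enter before any oxaliplatin and patients who enter after one dose differ in what that period contains. The second group received its first dose without the intervention. Depending on the length of the plan, it then has either one fewer chemotherapy-linked cycle of intervention or one more oxaliplatin dose behind it at the 3-month assessment.

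If the two entry types fall unevenly between arms of 28, some of the arm difference in CIPN-20 reflects entry type rather than acupuncture. The baseline score cannot fully correct this, because a symptom-free patient with one prior dose looks the same at baseline as a patient with none.

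**Working it through.** **1. The plan's own figures.** Section 16.3 gives 50 complete patients, a 0.7 SD difference, one-sided alpha 0.05 and 80% power. With 25 per arm, the normal approximation gives 79.7% and the exact noncentral t gives 78.7%. Inflating for 10% loss, 50 / 0.9 = 55.6, rounded up to 56. Both figures reproduce; the sample size is not at issue.

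**2. Cycles and sessions left on a minimum plan.**
- 12 weeks = 84 days, and 84 / 14 = 6 cycles.
- With one cycle already given: 6 − 1 = 5 cycles, so 5 × 2 = 10 of 12 sessions (83%) can coincide with chemotherapy.
- Taking the 12 planned sessions as the denominator, the threshold is 0.6 × 12 = 7.2, i.e. 8 sessions. Ten is enough, but the attendance needed within chemotherapy visits rises from 8/12 = 67% to 8/10 = 80%. Section 9.2 does not make up missed sessions.

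**3. Oxaliplatin doses by the 3-month assessment, at 85 mg/m² each.**

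| Entry type | Doses | Cumulative planned dose |
|---|---|---|
| No prior cycle | 6 | 6 × 85 = 510 mg/m² |
| One prior cycle, 6-cycle plan | 1 + 5 = 6 | 510 mg/m² |
| One prior cycle, longer plan | 1 + 6 = 7 | 7 × 85 = 595 mg/m² (595 / 510 = 1.17) |

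The shortfall in study cycles and the extra dose occur in different patients.

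**4. Chance imbalance in entry type.** The documents give no share p of patients entering after one cycle, so p is assumed. The 95% range for the difference between arms of 28 is ±1.96 × √(2p(1 − p) / 28):
- p = 0.10: 1.96 × 0.080 = ±16 points
- p = 0.30: 1.96 × 0.122 = ±24 points
- p = 0.50: 1.96 × 0.134 = ±26 points

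An exact hypergeometric check gives the chance of a gap of at least 20 points as about 2%, 12% and 18% for shares of 10%, 25% and 50%.

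**5. Effect on the primary comparison.** Suppose patients with a prior cycle differ by 0.2 to 0.5 SD in 3-month CIPN-20 (assumed). A 24-point gap then shifts the arm difference by 0.24 × 0.2 = 0.05 SD to 0.24 × 0.5 = 0.12 SD, against the 0.7 SD target.

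**6. Dilution.** Suppose the effect is proportional to cycles treated, and a share f of patients has only 5 of 6. The expected effect is 0.7 × (1 − f/6), which is 0.688, 0.671 and 0.642 SD for f = 10%, 25% and 50%. Exact-t power falls from 78.7% to 77.5%, 75.6% and 72.3%. This is an upper illustration, since it gives every patient with a prior cycle the minimum plan.

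**The case against.** The strongest reply is that little is lost. The 5-cycle case needs both a minimum plan and a prior cycle, and it disappears if the 3 months were meant to run from enrollment. Section 9.8 lets acupuncture continue to 3 months after oxaliplatin is discontinued. Randomization balances entry type on average, and a 56-patient pilot has reason to limit covariates. Much of this stands and keeps the point small. It does not remove it: section 7.1.1 does not give the enrollment-based count, sessions after the last oxaliplatin dose are no longer concurrent with it, and one binary term costs one degree of freedom.

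A reader might go further and infer any of the following, which the documents do not support:
- **That the adherence endpoint is capped below success.** Ten sessions exceed the 8 needed.
- **That the minimum-plan patient has more oxaliplatin.** The total is the same 510 mg/m².
- **That the final assessment falls 28 days after the last dose instead of 14.** That holds only if the 12 weeks in section 10.2 governs (day 85 − day 57 = 28). Under the ideal timing in section 9.9 it falls about day 71, again 14 days after.
- **That baseline adjustment removes neuropathy oxaliplatin has already caused.** Section 7.2.1 excludes patients with neuropathy at baseline, so little is left to remove, and the exclusion applies to both arms.

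It is also fair to say that requiring 6 further cycles gives every patient with a prior cycle a planned 7 doses. The eligibility wording alone is therefore not enough; the stratum and the model term are what handle that difference.

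**Conclusion.** The point holds in a limited form. As worded, section 7.1.1 admits a patient with 5 cycles left for a 6-cycle intervention, and a patient with one more oxaliplatin dose than others by month 3. Neither the randomization nor the primary model recognizes the difference. The harm is modest dilution and chance imbalance: about ±24 points if 30% enter after one cycle, and ±16 to ±26 over 10% to 50%. On the assumed 0.2 to 0.5 SD difference, a 24-point gap moves the estimate by 0.05 to 0.12 SD. The share, the size of that difference and the proportional-effect model are all assumptions. Reading this as systematic bias would go too far, because 1:1 randomization does not favor either arm. Severity is minor to moderate.

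**What to change.** - **Section 7.1.1:** state that the planned regimen is counted from randomization, with at least 6 biweekly cycles remaining.
- **CRF and sections 16.4 and 16.5:** record prior cycle (0 or 1), stratify the 1:1 randomization on it, and include it as one binary term in the primary regression.
- **Passages to reconcile:** the prior-cycle allowance with the synopsis criterion on prior neurotoxic chemotherapy; the allowance with the section 11.0 removal rule, which refers to cycle 1 of chemotherapy without saying whether that means study cycle 1; within section 11.0, required discontinuation on a regimen change that drops oxaliplatin with the option to continue acupuncture; and the 12-week timing in section 10.2 with the end-of-treatment window in section 9.9.

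The cost is one eligibility sentence, a two-stratum list and one degree of freedom. A few patients with a fixed 3-month plan who have already had cycle 1 become ineligible. If that would hurt accrual, recording and stratifying alone still addresses the imbalance, though not the 5-cycle case. The sample size stays at 56.
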